Around 47 million people worldwide are affected by dementia, and the number is projected to triple in 2050. Treatment that reverse the pathological changes in the brain is not available currently, but cognition of People with Dementia (PWD) could be improved through intervention. Among the three major approaches in cognitive intervention for PWD, namely cognitive training, cognitive rehabilitation, and cognitive stimulations, ² cognitive stimulation was the one that recommended for enhancing the cognitive functions of PWD by the UK's National Institute for Health and Clinical Excellence.³ Therefore, this study will apply an adapted intervention targeting on stimulating cognitive function of PWD—the Cognitive Stimulating Play Intervention (CoS-Play)—that involves the six mind-body functional domains advocated for enhancing cognition of PWD by Wong and colleagues in 2014.4 They include auditory music and rhythm, visuospatial and fine motor skills, language and verbal skills, executive functions, kinesthetic and gross motor skills, and social functioning. The CoS-Play Intervention will address the shortcoming of the heavy reliance on language of conventional cognitive stimulation programs, and focus on the application of play. Some evidence from the literature demonstrated that playing games is beneficial to PWD's selfconfidence, social engagement with other participants, cognition and behavioural symptoms, but the methodological quality of some studies were found to be generally inadequate and not anchored in a conceptual framework.⁵⁻⁶ This study will address theses knowledge gaps using a randomized controlled trial and employing both quantitative measures and qualitative interviews to evaluate the feasibility and preliminary efficacy of the intervention.

Objectives of the Study

By carrying out the intervention in local day-care centers in Hong Kong alongside a wait-list control group, the study aimed at exploring the feasibility of the Cognitive Stimulating Play Intervention (CoS-Play) as a means of cognitive stimulation for people with early to moderate dementia, and examining its preliminary effects on the cognitive functions.

Study Design and Procedures

Design

[figure not shown]
This is a randomized controlled trial employing quantitative pre-intervention and post-intervention assessment of participants, as well as qualitative interviews with staff members of 2 community day-care centers to evaluate the feasibility and preliminary efficacy of the

intervention. This design allows us to reflect on the utility of the intervention in real practice, which is particularly important during the developmental stage of a complex intervention.⁷

Population

Eligible participants will be community dwelling adults aged 60 or above with a medically confirmed diagnosis of any type of dementia (such as Alzheimer disease, vascular dementia, etc). Those who will be included as participants are people at the stage of early to moderate dementia (stages 4-6 according to the Global Deterioration Scale⁸), able to sit independently, and physically stable. Those with acute physical or mental illnesses will be excluded. Center staffs who will be assisting in the CoS-Play will be invited to take part in interviews so that their opinions on the implementation of the program could be solicited

Procedures

Study Outcomes

Quantitative outcomes

A trained research assistant who will be blinded to the group allocation will assess the cognitive functions of the participants using the Montreal Cognitive Assessment (MoCA), the Fuld Object Memory Evaluation (FOME), and the Modified Verbal Fluency test (embedded in the FOME), at baseline (T0), and immediately postintervention (T1).

- a. Montreal Cognitive Assessment (MoCA). The Hong Kong version of the MoCA will be used to measure the global cognitive functions of the participants. This instrument has high internal consistency (Cronbach a $\alpha = .767$), excellent inter-rater reliability (Intra-class Correlation Coefficient [ICC] = 0.987), and good construct validity as compared with the Mini Mental State Examination and Global Deterioration Scale. It consists of 11 items, and lower total scores refer to lower levels of cognitive function.
- b. Fuld Object Memory Evaluation (FOME). Participants' memory will be evaluated using the FOME.¹⁰ The participants will be asked to memorise and recall 10 items across 5 recall trials and a delayed recall trial. The instrument has been validated in the Hong Kong Chinese population and found to have better construct validity than the Mini Mental State Examination (r = 0.69-0.74), and to have test–retest reliability (ICC = 0.91-0.96).¹¹ Three FOME scores, namely total storage (possible range of 0-50), total retrieval (possible range of 0-50), and delayed recall (0-10) will be derived. Total storage represents the encoding function, while total retrieval and delayed recall refer to the retrieval function. Higher scores represent better memory.
- c. Modified fluid verbal fluency test. Verbal fluency will be assessed using the Modified Fuld Verbal Fluency test, 12 which was modified from the original Fuld Verbal Fluency test embedded in the FOME as a distraction task. Participants will be asked to name animals, fruits, and vegetables in 1 minute or 30 seconds. The construct validity was acceptable as compared with the Mini Mental State Examination (r = 0.76), and the test had good test–retest reliability (r = 0.74). Total scores are the sum of the items being recalled, with higher total scores referring to better verbal fluency.

Qualitative outcomes

The staff will be interviewed about their perceptions of: (a) the acceptability of the program, (b) the feasibility of integrating the program to the usual service operations of the center, (c) the practicality of the program, and (d) the effects of the program on participants.

The guiding questions will be as follows:

a. Acceptability.

What do you think about the acceptability or satisfaction of the intervention to people with moderate dementia?

b. Integration.

What would you think if the intervention were to be integrated into the normal routine of your center?

c. Practicality.

What are the practical concerns regarding the CoS-Play?

d. Efficacy.

What changes did you observe in the participants after they had participated in the CoS-Play?

Statistical Analysis Plan

Quantitative analysis

SPSS Statistics 23 will be used for all analyses. Data collection and entry will be conducted by a research assistant who will be blinded to the group allocations. The demographic data and the participants' performance at baseline will be compared with Fisher exact test for categorical data, and with the Mann-Whitney U test for continuous data to detect differences between intervention and control groups. Intention-to-treat methods will be used for all analyses. Missing values will be imputed with the last observation carried forward approach. Analysis of covariance (ANCOVA) will be used to examine whether there are significant differences between groups on the outcome measures after 8 weeks of the intervention, using its baseline measures as a covariate. A 2-sided significance test (P < .05) will be applied. The magnitude of the effects between the intervention and control groups will be displayed as a partial η^2 effect size.¹³

Qualitative analysis

A deductive content analysis approach will be used to analyze the transcribed interview verbatim in relation to the feasibility of the intervention, which is considered suitable for a detailed analysis of the 4 indicators of the feasibility of the intervention—acceptability, integration, practicality, and effects.¹⁴ The principle investigator and a trained research assistant will first immerse themselves in the data, decide on the analysis of manifest content together before coding the transcripts individually. After that, both of them will discuss discrepancies in the coding and will reach a consensus on the categories that will be generated.

References

- 3. National Institute for Health and Care Excellence. *Dementia: Supporting People with Dementia and their Carers in Health and Social Care (CG42)*. United Kingdom: National Institute for Health and Care Excellence; 2006. Updated 2016.

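### With only one assessment after baseline, last observation carried forward records every participant lost to follow-up as exactly unchanged and biases the group difference

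*Combined protocol and SAP*

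**What the plan says.** The study is described as a "randomized controlled trial employing quantitative pre-intervention and post-intervention assessment of participants", run "alongside a wait-list control group". Under Quantitative outcomes, the MoCA, the FOME and the verbal fluency test are given "at baseline (T0), and immediately postintervention (T1"). The text describes no assessment between these two. The design figure is not reproduced, but the text names only T0 and T1.

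Under Quantitative analysis, the SAP states: "Intention-to-treat methods will be used for all analyses", then "Missing values will be imputed with the last observation carried forward approach". Groups are compared by ANCOVA at 8 weeks, "using its baseline measures as a covariate", with a two-sided 0.05 test. The effect measure is given as follows: "The magnitude of the effects between the intervention and control groups will be displayed as a partial" η².

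The documents give no missingness assumption, expected loss rate, alternative method or sensitivity analysis.

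**The concern.** With two time points, LOCF has only one value to carry. A participant without T1 gets T1 = T0, and the model then adjusts that value for the same T0. The person enters as someone observed not to change, in whichever arm they were. In people with dementia at Global Deterioration Scale stages 4–6, no change is a substantive assumption, and the plan does not justify it.

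The efficacy aim is "examining its preliminary effects on the cognitive functions". The planned P value and partial η² both come from this ANCOVA, so every quantitative efficacy result depends on the rule. A real effect could be understated in the figures used to plan a larger trial, or a difference in loss between arms could look like an effect. With a waiting-list comparator, equal loss cannot be taken for granted.

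**Working it through.** **Inputs.** From the documents: two assessments, LOCF, ANCOVA adjusted for baseline, two-sided 0.05, partial η². The documents give no sample size, SD, correlation, expected change or loss rate, so there is no planned figure to reproduce. Assumed for illustration: SD 5, T0–T1 correlation 0.8, total N of 40 or 60 randomised 1:1, and loss of 5% to 30%.

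**Algebra.** Let m1 and m0 be the mean T0-to-T1 changes on intervention and control, and d1 and d0 the loss rates, with loss unrelated to scores. The true difference is m1 − m0. LOCF gives each lost participant a change of 0, and randomisation balances baseline on average, so:

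- expected LOCF difference = (1 − d1)m1 − (1 − d0)m0
- bias = d0·m0 − d1·m1

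*Equal loss d:* the expected difference is (1 − d)(m1 − m0). For a true 3.0, it is 0.95 × 3.0 = 2.85, 0.90 × 3.0 = 2.70 and 0.80 × 3.0 = 2.40 at 5%, 10% and 20% loss. If the true difference is zero, there is no bias.

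*Unequal loss with drift:*

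- No true effect, both arms −2, loss 30% intervention and 10% control: 0.1(−2) − 0.3(−2) = +0.4. Swapping the loss rates gives −0.4.
- True 0.50 (m1 = −1.0, m0 = −1.5), loss 30% and 10%: 0.7(−1.0) − 0.9(−1.5) = 0.65, away from zero.
- True 1.50 (m1 = −0.5, m0 = −2.0), loss 10% and 30%: 0.9(−0.5) − 0.7(−2.0) = 0.95, towards zero.
- If the control mean does not change (m0 = 0), the bias is −d1·m1, which is only towards zero. Bias in either direction therefore needs drift.

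Simulating the planned ANCOVA with 400,000 per arm matched this formula to within about 0.01. Observed-score ANCOVA recovered the true difference to within about 0.02 in every setting run.

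**Behaviour at trial size.** 6,000 simulated trials per setting; unequal loss is shown as intervention v control; partial η² is the median of t²/(t² + df).

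| Setting | True | LOCF estimate | LOCF performance |
|---|---|---|---|
| Equal loss 5% | 3.0 | 2.85 | coverage 94–95% |
| Equal loss 10% | 3.0 | 2.7 | coverage about 93.5%; η² 0.18 |
| Equal loss 20% | 3.0 | 2.4 | coverage 89% (N=40), 87% (N=60); η² 0.16 |
| Equal loss 20% | 1.5 | 1.2 | coverage 93% |
| 30% v 10% | 3.0 | 2.1 | coverage 84% (N=40), 78% (N=60); η² 0.12 |
| 30% v 10% or 10% v 30%, both arms −2 | 0 | +0.4 or −0.4 | type I error 7.5–8.9% |
| 20% v 10%, both arms −2 | 0 | about +0.2 | type I error 5.5–6.5% |
| Equal loss, or no drift | 0 | 0 | type I error 4.1–5.5% |

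With observed T1 scores, η² for a true 3.0 is about 0.21. A separate repeat gave the same picture: under 20% equal loss, observed-score ANCOVA had about 95% coverage; under 30% v 10% with a 2-point decline, its type I error was 4.5–5.0%, against 7.3% (N=40) and 8.2% (N=60) for LOCF. The false-positive problem grows with sample size: 12.1% at 60 per arm with the 2-point decline.

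**Standard error.** At N=40 with 20% loss and no effect, the LOCF model SE is 0.86, against 1.07 from observed scores and 0.96 had nobody been lost. The 0.86 matches LOCF's own sampling variation, but the method claims more precision with a fifth of outcomes missing than with none missing.

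**Loss driven by deterioration.** If those with worse T1 than expected are likelier to be lost (30% v 10%, no true effect), observed-score ANCOVA is biased by +0.5 (type I error 7.5–8.8%) and LOCF by +0.3 (6.0–7.3%). With a 1-point decline added, both are biased by about 0.5.

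**The case against.** The strongest case against has four parts.

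*Size.* Every magnitude above is assumed, and nothing in the documents shows that many T1 scores will be missing in an 8-week day-centre study. A true difference of 3.0 is 0.6 SD, and a 2-point decline in 8 weeks is 0.4 SD; both are large. With a true 1.5 and 30% v 10% loss, coverage is 90–91%. With a 1-point decline and that loss, type I error is between 5.0% and 6.3% at 15 to 30 per arm. One SD of 5 also cannot represent scales as different as 0–50 and 0–10. All of this stands: it limits what can be said about size but leaves the mechanism intact.

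*Total error.* At N=40, root mean squared error for LOCF against observed-score ANCOVA is 0.93 v 1.08 (true 1.5, 20% loss), 0.99 v 1.02 (true 3.0, 10%) and 1.09 v 1.07 (true 3.0, 20%). LOCF is often no worse on this measure, but it gets there by shrinking the estimate by an amount set by the loss rate.

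*The alternative can be worse.* With a true 1.5 and deterioration-driven loss, LOCF gives 1.33–1.35 and observed-score ANCOVA 1.97–2.00. This stands, and it is why a delta-adjusted analysis belongs in the fix. It does not favour LOCF, because neither method is reliable under that mechanism.

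*Conservatism and intention to treat.* LOCF is conservative only in some settings; with unequal loss and decline it can manufacture a benefit. Intention to treat does not require LOCF. Multiple imputation also keeps everyone randomised in the analysis.

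**Conclusion.** The concern holds. The plan's own two-visit schedule turns LOCF into baseline carried forward, and nothing else in the documents corrects for it. When loss is unrelated to scores, a non-zero difference shrinks by the loss rate if loss is equal. If loss is unequal and scores drift, the bias can take either sign. The mechanism and formula are certain. The size is not, because it depends on loss rates and changes that the documents do not give: negligible at 5% equal loss (2.85 for 3.0), material at 20% equal loss (2.4 for 3.0) or 30% v 10% (2.1 for 3.0), and absent if no T1 is missing. With equal loss and no true effect, the false-positive rate is not inflated. This should be fixed before analysis; it does not undermine the trial's design.

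**What to change.** In the Quantitative analysis section, replace LOCF as the main method and name one of these in advance:

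- **(a)** ANCOVA of T1 on randomised group and baseline, using all observed T1 scores. Partial η² then comes directly from the fitted model.
- **(b)** Multiple imputation of T1 within arm from baseline scores, pooled by Rubin's rules. The SAP should then give the number of imputations and say how partial η² will be obtained.

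State that either choice assumes missingness depends only on arm and baseline, and that participants are analysed in the group to which they were randomised. With (a), say explicitly how leaving out those without T1 fits the intention-to-treat statement.

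Add one delta-adjusted sensitivity analysis: impute missing T1, then lower the imputed values by a range of amounts set separately by arm. Fix the range for each outcome scale before the data are seen; the documents give no basis for a figure here. Report missing T1 by arm with reasons. Keep LOCF, if at all, only as a labelled sensitivity analysis.

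The cost is a paragraph of SAP text and modest extra analysis, with no new data or participants. The standard error is larger: 1.07 v 0.86 at N=40 with 20% loss and no effect, or 1.07/0.86 = 1.24 times. Under equal loss this cost no power: 76% for observed-score ANCOVA v 72% for LOCF (N=40, true 3.0, 20% loss).

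### Does the efficacy ANCOVA need a centre term because the trial appears to run in two day-care centres?

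*Combined protocol and SAP*

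**What the plan says.** The Quantitative analysis section of the SAP sets out the efficacy model: "Analysis of covariance (ANCOVA) will be used to examine whether there are significant differences between groups on the outcome measures after 8 weeks", with the baseline value of the same outcome as the only covariate ("using its baseline measures as a covariate"). The test rule is "A 2-sided significance test (P < .05) will be applied". Centre is not mentioned there.

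Centres are mentioned elsewhere. The Objectives say "By carrying out the intervention in local day-care centers in Hong Kong alongside a wait-list control group". The Design section says "This is a randomized controlled trial employing quantitative pre-intervention and post-intervention assessment of participants", together with "qualitative interviews with staff members of 2 community day-care centers". The Population section adds: "Center staffs who will be assisting in the CoS-Play will be invited to take part in interviews". Under Quantitative outcomes, "A trained research assistant who will be blinded to the group allocation will assess the cognitive functions of the participants".

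The number two is attached to the interviewed staff. Since those staff are the ones helping to deliver the programme, delivery in two centres is a fair inference, and participants drawn from both is a likely one. The available text does not give the unit of allocation, any stratification, the sample size or the numbers per centre. The design figure is not reproduced and no text survives under Procedures, so these details may exist in the source file. Their absence is not held against the plan.

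**The concern.** Where individuals are randomised within centres, many statisticians would put centre in the model. Two day-care centres may differ in case mix (any dementia type, Global Deterioration Scale stages 4 to 6), in the staff who assist, and in usual activities. A difference in post-intervention score that baseline does not explain then goes one of two ways:

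- With allocation balanced by centre, it stays in the error term. The standard error is overstated and the test is conservative.
- Without balance, part of it becomes chance variation in the arm estimate.

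A centre term would cost one degree of freedom and no new data. At stake is power in what is probably a small trial, across MoCA, the three FOME scores and verbal fluency.

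**Working it through.** The plan has no figure to reproduce: the available text gives no sample size, SD, power or centre effect.

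**Inputs.** From the SAP: ANCOVA with arm and baseline, two-sided 5%. Inferred from the Design and Population sections: two centres. Assumed: equal centres, 1:1 arms, total N from 20 to 60, true effect 0.8 within-centre residual SD, baseline slope 0.7, and a centre gap D, in residual SD after baseline adjustment, from 0 to 1.0.

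**Step 1. Noise due to centre.** The share of residual variance is (D²/4)/(1 + D²/4). For D = 0.46 this is 0.0529/1.0529 = 5%; for D = 1.0 it is 0.25/1.25 = 20%.

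**Step 2. Allocation balanced by centre.** The confidence-interval width with the term, relative to without, is t(.975, N−4) / [t(.975, N−3) × √(1 + D²/4)].

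- N = 20, D = 0: 2.1199/2.1098 = 1.005, so 0.5% wider.
- N = 40, D = 0.5: (2.0281/2.0262)/1.0308 = 0.971, so 2.9% narrower.

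**Step 3. Allocation not balanced by centre.** Arm and centre are then correlated by chance, with mean squared correlation 1/(N−1). Fitting centre multiplies the variance of the arm effect by about 1 + 1/(N−1); leaving it out multiplies it by about 1 + D²/4. With k = [t(.975, N−4)/t(.975, N−3)]² − 1, break-even is near D = 2√[1/(N−1) + k].

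- N = 20: 2√(0.0526 + 0.0096) = 0.50 SD.
- N = 40: 2√(0.0256 + 0.0019) = 0.33 SD.

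**Step 4. A moderate gap.** Assume a residual intraclass correlation ρ of 2% to 5%. The between-centre variance is ρ/(1−ρ), and the root-mean-square gap between two centres is √[2ρ/(1−ρ)]: √0.0408 = 0.20 SD to √0.1053 = 0.32 SD. Both values lie below the break-even points in Step 3. Simulation averaged over this range agrees: no gain at N = 40 and interval ratios of 1.006 to 1.03 at N = 20 to 32 without balance; a gain of about 0 to 1 power point with balance.

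**Step 5. Simulated power at N = 40** (40,000 replicates per cell), without v with the centre term:

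| Gap (SD) | Balanced by centre | Not balanced |
|---|---|---|
| 0.25 | 67.1% v 67.6% | 67.1% v 66.6% |
| 0.46 | 66.4% v 68.4% | 65.8% v 67.1% |
| 0.67 | 64.5% v 68.4% | 63.3% v 66.8% |
| 1.0 | 58.7% v 67.8% | 58.3% v 66.9% |

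At N = 20 without balance the term loses at D = 0 (37.4% v 35.6%), is level or slightly behind at 0.46 (35.8% v 35.5%), and gains at 0.67 (34.3% v 35.5%).

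**Step 6. Validity.** The mean estimate was 0.80 in every cell with a true effect of 0.8. At N = 40 the actual type I error of the planned test was 4.7%, 4.6%, 3.8% and 2.9% over the four gaps with balance, and about 5% without it. If whole centres were allocated, centre and arm would coincide and the term could not be fitted.

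**The case for a change.** The best argument for a change is the stratified case. If allocation was balanced by centre, the term costs almost nothing (0.5% of interval width at N = 20 when centre has no effect), and leaving it out pulls the actual type I error down to 2.9% at a gap of 1.0 SD with N = 40. Conventional practice is to adjust for a stratification factor. The sponsor knows the allocation scheme and could settle the condition at once. Naming the term in advance would also rule out a later choice between adjusted and unadjusted results.

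The stratified argument stands, but only as a conditional. Nothing available says that allocation was stratified or balanced by centre, so the analysis cannot be shown to ignore a design factor. Where it was, an analyst would ordinarily add the factor, and the omission errs on the conservative side. A residual gap of 1.0 SD is extreme once baseline is in the model, and one named blinded assessor gives no sign of rater differences between centres. The argument about later choices carries little weight, because the SAP already fixes one model for every outcome. A blanket request for the term would lower power over part of the range, as Steps 3 to 5 show.

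**Conclusion.** The SAP's ANCOVA can stay as written. It gives a valid comparison under individual randomisation, and the only possible loss is some precision. For residual centre gaps up to about 0.5 SD and N of 20 to 40, the centre term is worth about 0 to 2 power points if allocation is balanced by centre. Without balance it ranges from a loss of about 2 points (N = 20, no centre effect) to a gain of about 1 (N = 40, gap 0.46 SD). Reasonable statisticians would differ over such a trade-off, and it would hardly alter what a study of feasibility and preliminary effects can conclude.

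This rests on assumed sample sizes, equal centres, an effect of 0.8 SD and assumed centre gaps, since the documents give none of these. It would tip towards including centre if the full source showed allocation stratified by centre. The point does not arise if whole centres were allocated to arms or if one centre supplied every participant.
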